## PROTOCOL SYNOPSIS

Title:	Safety and Performance of Metastatic Tumor Cell Trap Device in Patients with Advanced Ovarian Cancer
Protocol Number:	MTRAP-2016-01
Medical Device:	Metastatic Tumor Cell Trap Device (M-Trap)
Intended Use:	M-Trap is an implantable medical device designed to capture disseminated tumor cells (DTCs). It is intended for use in advanced-stage ovarian cancer patients.
Surgical Use:	Up to three (3) M-Trap devices will be surgically implanted via laparotomy in the right and left paracolic (pelvic) gutters and behind segment 6 of the liver within the peritoneal cavity of the patient at the time of surgical resection. Patients will receive standard chemotherapy with carboplatin and paclitaxel. After completion of chemotherapy, M-Trap devices will be removed via minimally invasive surgery (laparoscopy) following the device removal protocol.
Study Design:	Prospective, multi-center, non-blinded, single-arm study. Safety and performance study conducted in accordance with ISO 14155.
Study Objective(s):	The study objective is to assess the safety and the performance of the MTrap device.  Safety objectives: The primary objective is to demonstrate that the safety of M-Trap, as measured by freedom from device- and procedure-related major adverse events through 6-months post-implantation, is non-inferior to historical controls.  The secondary objective is to collect long-term safety data to support device safety and post-market surveillance. Safety will be evaluated to demonstrate acceptable levels of device-related and procedure-related complications.  Performance objective: The primary objective is to confirm M-Trap performance, as determined by histological evidence of tumor cell capture. The secondary objective is to assess disease focalization with use of the M-Trap device.

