### **1.2. Novel Therapeutic Strategy**

The M-Trap Device (Metastatic Tumor Cell Trap Device) represents a breakthrough therapeutic strategy that provides a preferential site for the capture of disseminating tumor cells, transforming a systemic disease into a focalized disease where surgery, radiation, and chemotherapy have proven efficacy. M-Trap is an implantable surgical

mesh comprised of a non-resorbable, polycarbonate polyurethane (PCPU) scaffold with a Type I collagen coating.

M-Trap is intended to be implanted into the peritoneal cavity during the tumor debulking procedure to capture disseminating tumor cells. Up to three (3) M-Trap devices will be surgically implanted via laparotomy in the right and left paracolic (pelvic) gutters and behind segment 6 of the liver within the peritoneal cavity of the patient at the time of surgical resection. Patients will receive standard platinum-based chemotherapy. If the cancer is diagnosed to have recurred, M-Trap devices with captured tumor cells will be removed via minimally invasive surgery (laparoscopy).

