### 6.2.3. Device Removal Procedure

Following completion of chemotherapy treatment, M-Trap devices will be removed under one of following scenarios, whichever occurs first:

- (1) In the event of an adverse event necessitating device removal.
- (2) After disease progression as defined by objective RECIST 1.1 and CA-125 criteria. Both criteria must be met as follows:

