### **10.3. Analysis Methods**

The number of patients in all study populations, as well as the distribution by site will be presented. The reasons for interruption of patient follow-up will be listed and the average time of patient follow-up will be given. Descriptive statistical data will be used to summarize the characteristics of subjects at the time of inclusion (demographics, baseline and procedure data).

Quantitative parameters will be described using the following summary descriptive statistics at each time point: number of non-missing values, mean, standard deviation, median, first and third quartiles, and minimum and maximum values. Qualitative parameters will be described overall using frequencies and percentages. Percentages will be calculated on the number of non-missing observations. In order to provide unbiased and informative findings, no replacement of missing values is planned for any parameters. In all applicable cases, reported analysis will mention the number of missing values for each outcome relatively to the considered analysis set.

Analysis of safety will be performed on the ITT population and the As-Treated population. The primary safety endpoint will be analyzed using a unilateral one sample test for binomial proportion at the 5% level. In addition, the exact bilateral 95% confidence interval will also be given. The statistical test for the primary safety endpoint is given by:

- H0: M-Trap freedom MAE incidence  $\leq$  90% - Non inferiority margin (25%)  
Versus
- HA: M-Trap freedom MAE incidence  $>$  90% - Non inferiority margin (25%)

The primary performance endpoint is the percentage of recurrent patients with histological evidence of tumor cell capture in at least one M-Trap device. The secondary performance endpoints are the percentages of recurrent patients with disease focalization scores of: 1) I, 2) I or II, 3) I, II or III, and 4) I, II, III or IV. Analysis of performance will be performed on the As-Treated population. The primary performance and secondary endpoints will be assessed with exact one-sided 90% confidence intervals.

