2.4.4. Follow-up Patients characteristics

Descriptive statistical data will be used to draw up a recapitulation of patients' follow-up visit characteristics.

The following data will be presented on the as-treated population at 1Month, 3Months, 6Months, 9Months, 12Months, 15Months and 18Months follow-up visits:

- Physical exam: Weight (kg), BMI (kg/m²), Temperature (°C), Blood pressure (Systolic and Diastolic in mmHg), Heart rate (bpm), Specific abdominal examination performed (Yes/No), Presence of nodules or bumps if Yes (Yes/No) and How many nodules or bumps if Yes, Specific gynecologic examination performed (Yes/No), Presence of nodules or bumps in the cul-de-sac if Yes (Yes/No) and How many nodules or bumps in the cul-de-sac if Yes.
- Chemotherapy: Is chemotherapy complete (Yes/No), Number of IDS patients complete chemotherapy by the 3-month visit, Number of PDS patients complete chemotherapy by the 6-month visit, Number of cycles received since last visit, Is this visit the first one since the completion of chemotherapy (Yes/No), The reasons if chemotherapy is not completed
- Biomarker CA-125: CA-125 test performed (Yes/No), CA-125 results (U/mL), Disease progression as defined by CA-125 criteria (Yes/No).
- CT Scan: Abdominal CT Scan obtained, Pelvic CT Scan obtained, Chest CT Scan obtained, Target lesions site, Target Lesion location, Target Lesion Measurement (mm), New Target lesion, Evaluation of Target Lesions after chemotherapy completion, Non-Target Lesion Sites, Non-Target

STATISTICAL ANALYSIS PLAN

lesion location, Measurement of Non-Target lesion if measurable (mm), New Non-Target lesion, Evaluation of Non-Target Lesions after chemotherapy completion, Objective Subject Response.

CT Scan is not performed at 1Month visit.

- Device(s) Removal: Device(s) removal planned during this visit (Yes/No)
- Ultrasound: Abdominal Ultrasound obtained (Yes/No), The reason specification if No
- Medications: Medication(s) change since last visit (Yes/No)
- Adverse Event: New adverse events occur since last visit (Yes/No)

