2.4.5. Primary Analysis

Primary analysis of safety will be performed on the ITT population and the As-Treated populations.

The primary safety endpoint is freedom from device and procedure-related major adverse events through 6-months post-implantation, including shock, cardiac arrest, myocardial infarction, pulmonary embolism, prolonged intubation, unplanned reintubation, or adverse events leading to removal of the device, including infection, seroma formation, mesh migration, bowel obstruction, adhesions, and local cancer progression through the abdominal wall at M-Trap suture sites.

The primary safety endpoint will be analyzed using a unilateral one sample test for binomial proportion at the 5% level. In addition, the exact bilateral 95% confidence interval will also be given. The statistical test for the primary safety endpoint is given by:

- H0: M-Trap freedom MAE incidence \leq 90% - Non-inferiority margin (25%)
- Versus
- HA: M-Trap freedom MAE incidence $>$ 90% - Non-inferiority margin (25%)

A modified primary analysis will also be performed that uses a freedom from MAE incidence rate that is adjusted for the surgical complexity of the study population, as compared to the Patankar study population, which is the basis of the statistical rationale for this study (repeated in the table below). The total number of extended procedures will be split in four classes: 0, 1, 2, 3 and more.

Procedures	0	1	2	3 or more	AVG
Total patients	1352	1214	254	50	2870
Severe complications, n	51	92	44	9	196
Severe complications, %	3.8%	7.6%	17.3%	18.0%	6.8%

A further modified primary analysis will also be performed that only includes procedure-related events through 30 days, as this is the comparable population to the Patankar study population, which is the basis of the statistical rationale for this study.

Primary analysis of performance will be performed on the As-Treated population and by device location. This analysis will be also performed using these 3 following sub-populations: (1) platinum resistant, recurrent patients; (2) platinum sensitive, recurrent patients; (3) non-recurrent patients (see definition in part 2.5).

The primary performance endpoint is histopathologic evidence of tumor cell capture (see 2.5). Histopathology will be performed after device explant.

The primary performance endpoint will be assessed with exact one-sided 90% confidence intervals.

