Add 1 to the score if Large bowel resection is ticked (colectomy, rectosigmoid resection).

Add 1 to the score if Diaphragm peritonectomy or Full-thickness diaphragm resection (diaphragm resection) is ticked.

Add 1 to the score if Partial hepatectomy (hepatic resection) is ticked.

- Derived criterion “freedom of device- and procedure-related major adverse events through 6 months post-implantation, including shock, cardiac arrest, myocardial infarction, pulmonary embolism, prolonged intubation, unplanned reintubation, or adverse events leading to removal of the device, including infection, seroma formation, mesh migration, bowel obstruction, adhesions, and local cancer progression through the abdominal wall at M-Trap suture sites” which is the primary endpoint will be calculated as follows:

If a MAE occurred in a patient within 6 months \pm 2W post implantation and “Does this event meet the definition of a major adverse event for the primary endpoint?” = “Yes” then “freedom of device- and procedure-related major adverse events through 6-months post-implantation” = “No” else “freedom of device- and procedure-related major adverse events through 6-months post-implantation” = “Yes”.

- Derived criterion “recurrent patients” will be defined as patients with device removal reason “Disease progression as defined by objective RECIST 1.1 and CA-125 criteria” or device removal reason “other” that indicates recurrence. Derived criteria “non-recurrent patients” are the remaining patients. CRO will send to MTrap an excel file with the list of all other reason of device removal to identify the reason that indicates “recurrence”.
- Derived criterion “time to recurrence” will equal to the date of the follow-up visit when “Device removal planned for this visit” is yes minus the procedure date.
- Derived criterion “platinum resistant, recurrent patients” will be defined as “recurrent patients” where the difference between the date of the follow-up visit when “Device removal planned for this visit” is yes and the date of the most recent chemotherapy medication treatment is less than or equal to 180 days.
- CRO will send to MTrap an excel file with the list of the concomitant medication to identify the chemotherapy medication treatment. Derived criterion “platinum sensitive, recurrent patients” will be defined as “recurrent patients” that are not “platinum resistant, recurrent patients”.

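### The sponsor decides, without a written criterion and without being kept from the outcome data, which removals for reason other count as recurrence, and this sets the denominator of the focalization endpoints

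*SAP*

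**What the plan says.** **Who is recurrent.** SAP 2.5 gives two routes. The first is removal coded as disease progression by RECIST 1.1 and CA-125; Protocol 6.2.3 asks for the two together ("Both criteria must be met as follows"). The second is removal for reason *other* where that reason indicates recurrence. For the second route, "CRO will send to MTrap an excel file with the list of all other reason of device removal to identify the reason that indicates" recurrence. MTrap is the sponsor. Non-recurrent patients "are the remaining patients".

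**What is not said.** SAP 2.5 gives no criterion for reading an *other* reason, names no independent reader, and does not place the step before or after the outcome data. The synopsis describes a "Prospective, multi-center, non-blinded, single-arm study".

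**Where the classification is used.**
- Protocol 10.3: "The primary performance endpoint is the percentage of recurrent patients with histological evidence of tumor cell capture in at least one M-Trap device". The secondary endpoints there are also percentages of recurrent patients.
- SAP 2.4.6 keeps recurrent patients as the denominator for the four focalization endpoints.
- SAP 2.4.5 differs for the primary endpoint: "Primary analysis of performance will be performed on the As-Treated population and by device location". It then repeats the analysis in platinum-resistant recurrent, platinum-sensitive recurrent and non-recurrent patients.
- SAP 2.4.7 censors, in the time-to-recurrence Kaplan-Meier curve, patients whose devices were removed before 18 months for a reason other than recurrence.

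**Removal trigger.** Protocol 1.2 puts it more simply than 6.2.3: "If the cancer is diagnosed to have recurred, M-Trap devices with captured tumor cells will be removed". Protocol section 2 and SAP 1.3.2 say the same.

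**The concern.** A denominator should be fixed without knowledge of the numerator. Here the order of events works against that. The removal reason exists only once removal is planned or done. The same operation yields the focalization score (Protocol 6.2.3) and the specimen. Local pathology comes before shipment to the core laboratory, which then enters tumor cell infiltration (SAP 2.4.7). By the time a list of *other* reasons can be drawn up, some or all of these results may be known, and nothing keeps them from the person who reads the list.

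The second route is likely to matter because the coded route is narrow. A recurrence seen on CT alone or on CA-125 alone does not meet both criteria, while three passages describe removal whenever recurrence is diagnosed. The SAP itself foresees *other* removals that mean recurrence.

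If a patient without capture, or with a poor focalization score, is read as non-recurrent, the recurrent-patient percentages rise. In the Kaplan-Meier curve the same decision turns an event into a censored time. Even when every reading is fair, the result is open to challenge, because the step was not pre-specified.

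**Working it through.** **1. Design figures.** The documents give no sample size, target or threshold for performance. The only design figure is for safety: n = 20, success at 17 or more event-free, null rate 0.90 − 0.25 = 0.65. The exact binomial gives one-sided alpha 0.044 and power 0.867, so the stated power above 85% reproduces. It has no bearing on this point.

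**2. How many recurrent patients.** Protocol 1.5 puts progression at about 40–50% at 12 months. Assuming a constant hazard, the proportion at 18 months is 1 − (1 − p)^(18/12):
- p = 0.40: 1 − 0.60^1.5 = 53.5%; × 22 = 11.8 patients
- p = 0.50: 1 − 0.50^1.5 = 64.6%; × 22 = 14.2 patients

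Fewer would meet both removal criteria. A denominator of roughly 8 to 14 is plausible.

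**3. Effect of one or two readings.** The lower limit is the exact one-sided 90% limit, the 10th percentile of Beta(x, n − x + 1). Assume 11 recurrent patients with 9 captures, the two without capture having been removed for reason *other*:

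| *Other* removals read as non-recurrent | Result | Lower limit |
|---|---|---|
| none | 9/11 = 81.8% | 58.5% |
| one | 9/10 = 90.0% | 66.3% |
| both | 9/9 = 100% | 77.4% |

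Two readings move the estimate by 18 points and the limit by 19.

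**4. A second set of assumptions.** Take 8 coded recurrences (6 with capture) and 4 *other* removals (2 with capture, 2 without):

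| *Other* removals counted as recurrent | Result | Lower limit |
|---|---|---|
| none | 6/8 = 75.0% | 46.2% |
| all four | 8/12 = 66.7% | 44.1% |
| only the two with capture | 8/10 = 80.0% | 55.0% |
| only the two without capture | 6/10 = 60.0% | 35.4% |

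Selection on the outcome gives a value outside the range from none (75.0%) to all (66.7%). A main result above or below both would therefore be a visible warning.

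**5. Worst case over repeated trials.** Suppose every patient has the same true capture rate, there are 8 coded recurrences, and only *other* removals with capture are admitted. Summing over all binomial outcomes, for 2, 3 or 4 *other* removals:

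| True rate | Expected estimate | Trials with lower limit above the true rate |
|---|---|---|
| 30% | 34.5%, 36.6%, 38.5% | 12.7%, 15.4%, 18.3% |
| 50% | 55.3%, 57.5%, 59.6% | 11.7%, 13.1%, 15.1% |
| 70% | 74.3%, 76.1%, 77.6% | 5.8%, 5.8%, 10.5% |

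The nominal maximum for the last column is 10%.

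**6. What is not exposed.** SAP 2.5 derives histopathologic capture per patient from infiltration above zero in at least one device, with no condition on recurrence. SAP Tables 58 and 59 are on the As-Treated population. No reading of an *other* reason changes the overall As-Treated percentage.

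**The case against.** **The primary endpoint.** A reader might infer that the sponsor chooses the denominator of the primary performance endpoint outright. The SAP does not support that: its primary analysis covers all As-Treated patients, and recurrence only splits sub-populations. The inference holds only for the endpoint as Protocol 10.3 words it. This objection stands and limits the point.

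**Visibility.** A patient read as non-recurrent does not vanish. The SAP reports the non-recurrent group separately and focalization overall as well, tabulates removal reasons (Table 90), and lists primary performance, secondary performance and removal data (Listings 22, 25, 26). This makes a shift traceable, but it does not stop the recurrent-patient percentages from depending on it.

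**No shown bias.** A reader might also infer that classification will follow the outcome. The documents do not show this. The file described is a list of reasons, nothing says it carries histology, and that the reasons are free text is itself an inference. Images go to the DSMB for confirmation (Protocol 6.6.4 and 6.6.5), though no text links that review to the recurrent class. What the documents show is an unprotected opportunity.

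**Consequence and size.** The performance endpoints carry no hypothesis or threshold, so no formal decision turns on this. The number of *other* removals is not given and may be zero. Both objections stand.

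**A mechanical replacement.** Applying CT response or the CA-125 flag to *other* removals alone would miss recurrence shown by biopsy or examination. It would also treat adverse-event and 18-month removals with one-criterion progression differently. That is a fair objection to a purely mechanical rule, so the fix below is broader.

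**Conclusion.** The concern holds in limited form. SAP 2.5 leaves the recurrent class, for *other* removals only, to an unwritten sponsor judgement that may be made with the outcome in view. This exposes:
- the secondary focalization endpoints;
- the recurrence sub-populations of the primary performance analysis;
- the event or censoring status in the time-to-recurrence curve;
- the primary performance endpoint as Protocol 10.3 words it.

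The SAP's overall As-Treated capture result is unaffected. Removals coded as RECIST 1.1 plus CA-125 progression need no sponsor reading.

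The size cannot be derived from the documents. Under the assumed counts, two readings move a recurrent-patient percentage from 82% to 100% and its lower limit from 58% to 77%; with no *other* removals the effect is nil. The harm is to the interpretation and credibility of these endpoints, since no pass/fail rule depends on them. The gap should be closed before the data are read. It is not evidence that any result will be biased.

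**What to change.** 1. **SAP 2.5.** Replace the open reading of *other* reasons with written criteria. Base them on items already collected at follow-up (SAP 2.4.4), namely the CT Objective Subject Response and the CA-125 item, "Disease progression as defined by CA-125 criteria (Yes/No"), together with any other recorded evidence of recurrence.
2. **Masking and timing.** Whoever classifies should have no access to infiltration or focalization data. The dated classification file should be locked before those data are released.
3. **Sensitivity analyses** of the recurrent-patient endpoints: one counting only removals coded as RECIST 1.1 plus CA-125 progression, and one counting all *other* removals as recurrent. The second is deliberately over-inclusive and serves as a comparison, not as an estimate.
4. **Denominator.** Reconcile Protocol 10.3 (recurrent patients) with SAP 2.4.5 (As-Treated) for the primary performance endpoint, and state which one is primary.
5. **Removal trigger.** Protocol 1.2, section 2 and 6.2.3 and SAP 1.3.2 must be reconciled with each other. The changes above leave the removal rule as it is.

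The cost is SAP wording, one dated file and a little extra analysis; no new data are needed. A few patients may be classed differently from the investigator's impression.

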#### Gynecological Cancer Intergroup criteria

- i. Patients with elevated CA-125 pretreatment and normalization of CA-125 must show evidence of CA-125 greater than, or equal to, 2 times the upper limit of the reference range on 2 occasions at least 1 week apart, or
- ii. Patients with elevated CA-125 before treatment, which never normalizes, must show evidence of CA-125 greater than, or equal to, 2 times the nadir value on 2 occasions at least 1 week apart, or
- iii. Patients with CA-125 in the reference range before treatment must show evidence of CA-125 greater than, or equal to, 2 times the upper limit of the reference range on 2 occasions at least 1 week apart.

- (3) At the final 18-month post-implantation time point.

\* Baseline is defined as the follow-up time point following completion of chemotherapy treatment.

Device removal will be performed via minimally invasive surgery (laparoscopy) following the institution's standard protocols. To remove the device, M-Trap device(s) will be located, carefully segregating the device with any captured tumor cells from the surrounding tissues. Next, a single-use specimen retrieval system (Endobag™ container) will be placed to recover the extracted M-Trap device through the 15mm trocar cannula of the laparoscopic port, maintaining the integrity of the device for histological analysis.

The laparoscopy will be completed following the institution's standard protocols. An assessment of the device removal procedure will occur at the time of explant, including ease of locating and removing the M-Trap device and the occurrence of any device- or procedural-related AEs during the removal procedure. If for some reason the device(s) cannot be explanted through laparoscopy, the surgeon should proceed using best clinical judgement, including a potential conversion to laparotomy.

Semi-quantitative scoring of disease focalization based on direct visual assessment, CT scan and ultrasound will be performed at the time of device removal, using the following scale:

Degree of Disease Focalization	Definition
I	Approximately 100% of recurrent disease contained in M-Trap devices
II	Approximately 75% of recurrent disease contained in M-Trap devices
III	Approximately 50% of recurrent disease contained in M-Trap devices
IV	Approximately 25% of recurrent disease contained in M-Trap devices
V	No obvious recurrent disease contained in M-Trap devices

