1.3.2. Study Device Use

The M-Trap Device (Metastatic Tumor Cell Trap Device) represents a breakthrough therapeutic strategy that provides a preferential site for the capture of disseminating tumor cells, transforming a systemic disease into a focalized disease where surgery, radiation, and chemotherapy have proven efficacy. M-Trap is an implantable surgical mesh comprised of a non-resorbable, polycarbonate polyurethane (PCPU) scaffold with a Type I collagen coating.

M-Trap is intended to be implanted into the peritoneal cavity during the tumor debulking procedure to capture disseminating tumor cells. Up to three (3) M-Trap devices will be surgically implanted via laparotomy in the right and left paracolic (pelvic) gutters and behind segment 6 of the liver within the peritoneal cavity of the patient at the time of surgical resection. Patients will receive standard platinum-based chemotherapy. If the cancer is diagnosed to have recurred, M-Trap devices with captured tumor cells will be removed via minimally invasive surgery (laparoscopy).

	STATISTICAL ANALYSIS PLAN	MTRAP_SAP_v2.0_FINAL redacted.docx
		MTRAP
		Page 8/9

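### The SAP's platinum-resistance rule counts from the most recent chemotherapy of any kind to the planned-removal visit, so it can put recurrent patients in the wrong platinum subgroup

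*SAP*

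**What the plan says.** SAP 2.5 measures "the difference between the date of the follow-up visit when" device removal is marked as planned and the last chemotherapy record. A recurrent patient is platinum resistant when the time since "the date of the most recent chemotherapy medication treatment is less than or equal to 180 days". Platinum sensitive is the complement: it "will be defined as “recurrent patients” that are not “platinum resistant, recurrent patients".

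Chemotherapy records are picked out by a sponsor review: "CRO will send to MTrap an excel file with the list of the concomitant medication to identify the chemotherapy medication treatment". No criterion for line, agent or timing is written for that review.

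The flag feeds SAP 2.4.5, where capture is broken down by "1) platinum resistant, recurrent patients; (2) platinum sensitive, recurrent patients; (3) non-recurrent patients". SAP 2.4.6 and 2.4.7 use the same groups for focalization.

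Three other parts of the plan bear on the interval:

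- **Study chemotherapy.** SAP 1.3.2: "Patients will receive standard platinum-based chemotherapy".
- **Removal for progression.** Protocol 6.2.3 requires RECIST 1.1 and CA-125 progression together ("Both criteria must be met as follows"), and the CA-125 criterion needs raised values "on 2 occasions at least 1 week apart".
- **Time to recurrence.** SAP 2.5 dates this from the same planned-removal visit.

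**The concern.** A label of platinum resistance is meant to say how soon disease returned after platinum. The SAP interval has neither of the end points which that meaning needs. It starts at whichever chemotherapy was last recorded, and it ends at an administrative visit rather than at progression.

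Either end can move independently of the patient's response to platinum. A later start (second-line drug) shortens the interval and favours the resistant label. A later end (removal planned some visits after progression) lengthens it and favours the sensitive label. Because sensitive is defined as the remainder, every wrong label alters both groups, and both are small.

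**Working it through.** The plan states no figure that depends on this rule, so there is none to reproduce. The check applies the rule to the visit schedule and to example timelines.

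**Inputs.** Visits at 3, 6, 9, 12 and 15 months fall nominally on days 91, 183, 274, 365 and 457 (30.4375 days per month). Chemotherapy ends before the 3-month visit after interval debulking and before the 6-month visit after primary debulking (schedule footnotes). Concomitant medication is at the investigator's discretion (Protocol 6.5). Patients are followed to 18 months even after early removal (Protocol 6.2.3). The exact chemotherapy dates below are assumed.

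**1. How close the visit schedule sits to day 180.** Assume the last dose was 0 to 28 days before the post-chemotherapy baseline visit.

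- Interval debulking, last dose on day 91 to 63. To the 6-month visit: 183 − 91 = 92 to 183 − 63 = 120 days, resistant. To the 9-month visit: 274 − 91 = 183 to 274 − 63 = 211 days, sensitive.
- Primary debulking, last dose on day 183 to 155. To the 9-month visit: 274 − 183 = 91 to 274 − 155 = 119 days, resistant. To the 12-month visit: 365 − 183 = 182 to 365 − 155 = 210 days, sensitive.

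At nominal dates, one visit between progression and planned removal is enough to change the label. A visit early in its one-month window can still fall at or below 180 days.

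**2. Example timelines.** Interval debulking, last platinum on day 77.

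| Timeline (assumed) | SAP rule | Last platinum to CT progression | Last platinum to both criteria met |
|---|---|---|---|
| A. CT progression day 183; CA-125 criterion met and removal planned day 274 | 274 − 77 = 197, sensitive | 183 − 77 = 106, resistant | 274 − 77 = 197, sensitive |
| B. CT progression day 365; second line to day 440; both criteria met and removal planned day 457 | 457 − 440 = 17, resistant | 365 − 77 = 288, sensitive | 457 − 77 = 380, sensitive |
| C. Both criteria met and removal planned day 365; chemotherapy after removal to day 520 | 365 − 520 = −155, resistant | 365 − 77 = 288, sensitive | 365 − 77 = 288, sensitive |

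Timelines B and C are mislabelled on either reading of progression. Timeline A is mislabelled only if CT progression alone counts. C arises only if the most recent chemotherapy is taken literally from the final database.

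**3. Effect of moving one patient.** Protocol 1.5 gives about 40% to 50% progressing at 12 months: 0.40 × 20 = 8 to 0.50 × 22 = 11 recurrent patients. Subgroups of 3 to 8 are an assumption.

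Take x captures in n patients and move one patient out. If she had no capture, x/n becomes x/(n−1), a rise of x/[n(n−1)]. If she had capture, x/n becomes (x−1)/(n−1), a fall of (n−x)/[n(n−1)]. Each is at most 1/n: 1/8 = 12.5 points and 1/3 = 33.3 points. The largest shift from moving one patient in is 1/(n+1), which is smaller. The shift is zero when the moved patient's outcome matches a group with all or no captures.

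Illustration for the resistant group, starting at 4/5. The exact one-sided 90% lower bound is the 0.10 quantile of Beta(x, n−x+1).

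| Change | Percentage | Lower bound |
|---|---|---|
| None: 4/5 | 80.0% | 41.6% |
| Captured patient moves out: 3/4 | 75.0% | 32.0% |
| Captured patient moves in: 5/6 | 83.3% | 49.0% |
| Non-captured patient moves out: 4/4 | 100% | 56.2% |

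The shifts here are about 3 to 20 points.

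**The case against.** The best defence is that the rule will usually give the right answer. Study chemotherapy is platinum-based, so for anyone with no further treatment the most recent chemotherapy is first-line platinum. The device is meant to come out when recurrence is diagnosed, CT and CA-125 are scheduled at the same visits from 3 months, and the SAP also accepts recurrence recorded under another removal reason, so detection and planned removal will often share a visit. The protocol's progression trigger for removal needs both criteria, so a patient with CT progression alone has arguably not yet progressed. The sponsor's list review could also exclude later-line drugs.

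Much of this stands. A reader might infer that second-line treatment or late removal does misplace patients as a matter of course. The documents do not support that: they do not say how often chemotherapy would start with devices in place, or how often removal would be planned after progression. A reader might also take 12 to 33 points as the usual effect of one wrong label, but 1/n is the ceiling.

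What does not stand is the idea that the text already protects the label. The list review has no written criteria, nothing bars chemotherapy after progression from setting the start date, and no other section corrects the rule. The both-criteria argument answers timeline A but not B or C.

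**Conclusion.** The rule as written can give a wrong label in either direction. Chemotherapy after progression can make a patient resistant whichever definition of progression is used. The opposite error needs removal to be planned at a visit later than first documented progression, and in the case worked above it turns on whether RECIST progression alone counts.

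The reach is narrow. Only the resistant/sensitive split of capture and focalization is affected. The capture rate in all recurrent patients (Protocol 10.3, which does not mention platinum status), the combined focalization analyses and the primary safety test with its n=20 do not use the flag. It would be wrong to infer that the primary performance result is compromised.

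Within the split, one moved patient shifts a percentage by between 0 and 12.5 points (n=8) or 33.3 points (n=3). This rests on assumed subgroup sizes; the 40% to 50% is a 12-month rate while follow-up runs to 18 months. Frequency is unknown. This is a minor point, worth correcting because it is cheap.

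**What to change.** In SAP 2.5:

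- Start the interval at the last dose of the first-line platinum-based regimen given before progression, with the date taken from the medication listing. The per-visit chemotherapy fields in SAP 2.4.4 list completion and cycles but no last-dose date.
- End it at the date of first documented progression. State whether that means RECIST progression alone or the visit at which both RECIST and CA-125 criteria are met, using the CT response and CA-125 progression fields in SAP 2.4.4. Say how the CA-125 date is set when two readings are needed.
- Use the same progression date for time to recurrence, so that the SAP does not carry two recurrence dates.
- Write the rule before the sponsor reviews the chemotherapy listing, so that labels are not decided case by case.

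This changes an analysis definition only: no new data collection, and no change to treatment or to when devices are removed. The cost is a few sentences and some extra derivation work. The progression date will still be limited by the three-monthly visits.
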